## List of Abbreviations

CRF	Case Report Form
CTRL	Center for Translational Research in Aging and Longevity
DXA	Dual-energy X-ray Absorptiometry
EAA	Essential Amino Acid
EDTA	Ethylenediaminetetraacetic acid (a blood preservative)
FDA	Food and Drug Administration
GC-MS	Gas Chromatography-Mass Spectrometry
GRAS	Generally Regarded as Safe
RIOA	Reynolds Institute on Aging (UAMS)
IRB	Institutional Review Board
LC-MS	Liquid chromatography-mass spectrometry
LOA	Limits of agreement
NB	Net balance
PB	Protein breakdown
PI	Principal Investigator
PS	Protein synthesis
SP	study product or placebo
TE	Total error
SEE	Standard error of the estimate
UAMS	University of Arkansas for Medical Sciences
IV	Intravenous catheter

## Study Schema

Study staff will recruit subjects via word of mouth to friends, family and colleagues.

Informed consent process takes place during Visit 1, followed by DXA scan.

Randomized subjects undergo two separate 7-hour study visits.

Visits 2 and 3 entail serial blood sampling from an IV catheter, ingestion of stable isotopes of amino acids every 10 minutes, and ingestion of SP (study product or placebo).

Blood samples analyzed at completion of study visits.

## Study Calendar

Procedure	Visit 1	Visit 2	Visit 3
Informed consent	x		
Fasted prior to visit		x	x
Blood sampling		x	x
IV		x	x
Ingest stable isotopes		x	x
Ingest SP		x	x

---

### 1.0 Protocol Summary

---

This will be a double-blinded, randomized, crossover pilot study to evaluate the validity of a continuous oral sip-feeding of stable isotope tracer method for the evaluation of whole-body protein metabolism. This method will be evaluated using two different amounts of an essential amino acid (EAA) + whey protein supplement on up to ten younger, healthy subjects. Stable isotope preparations will be continuously consumed by subjects throughout visits 2 and 3 to enable whole body protein metabolism to be measured. A DXA scan will be performed to quantify subject's lean mass.

---

### 2.0 Background

---

Stable isotope tracers are routinely used to study protein metabolism in free-living individuals in the fields of nutrition and exercise (1, 2). Whole-body rates of protein synthesis (PS), breakdown (PB), and net balance (NB) in response to nutrition and exercise interventions are commonly evaluated using a primed-constant infusion of essential amino acid (EAA) tracers, typically  $^{2}\text{H}_5$ -phenylalanine and  $^{2}\text{H}_4$ -tyrosine (1). This method has many advantages. The primed-constant infusion allows for determination of basal protein kinetics, in addition to the acute physiological response to an intervention, which allows for each subject to serve as their own control. Although an effective method, administration of the primed-constant infusion requires involvement from multiple trained individuals, including research pharmacists and nurses who compound and administer the EAA tracer. This limits the ability to apply these methods in field-type settings outside of a hospital or lab. The cost associated with purchase and

compounding of the tracer, in addition to involvement from multiple specialists, makes these types of studies very expensive and difficult to conduct.

An alternative to primed-constant infusion is to orally ingest amino acid tracers in sip fashion to achieve a similar plateau enrichment. Oral bolus ingestion of amino acid tracer has been used to quantify 24-hour whole-body protein metabolism in a variety of healthy and clinical populations for over 50 years (3). This method is one of the most conducive field-methods for determining whole-body protein metabolism in free-living subjects and has minimal participant burden. However, full integration of the tracer from a single bolus ingestion into the entire protein pool takes at least 10 hours. This limits the ability to quantify acute changes in protein kinetics of acute exercise or nutritional interventions. However, ingestion of a priming bolus, followed by continuous ingestion of EAA tracer may achieve steady-state equilibrium similar to constant infusion of the isotope. Thus, oral ingestion may enable the determination of acute changes in protein kinetics in the same respect as constant infusion. If shown to be valid, this method would significantly reduce the rigor and expense of pharmacy-prepared infusions, and more importantly, allow for quantification of acute physiological protein responses within the field setting.

---

### **3.0 Specific Aims**

---

SA1: To evaluate the validity of a continuous oral sip-feeding method of stable isotope tracer for the evaluation of whole-body protein metabolism in response to two different doses of an EAA/whey protein supplement (Low=6.3g and High=12.6g). We will compare kinetic responses with oral isotope ingestion to those previously determined by constant infusion with the same SP (4).

---

### **4.0 Study Population**

---

Up to 10 subjects of any gender or ethnicity will be enrolled with a target of n=10, 50% female for study completion. Subjects' duration of participation is approximately 2 weeks.

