#### **4.4 Subject Compensation**

Subjects will be compensated \$15 for Visit 1 and \$100 each for Visits 2 and 3. They will be mailed a check through UAMS SAP for their amount based upon visits attended.

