#### **4.7 Randomization**

SP grouping will be predetermined before the first enrollment takes place. Study staff will document enrollment information into a spreadsheet that contains the SP group designations. SP labels will contain these designations. In the event that subject dropouts or screening failures skew the balance of groups, the groups will be modified toward the end of the enrollment period so that balance will be regained at the conclusion of the study.

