#### **5.1 Blood Sample collection**

Study staff will collect approximately 2mL of whole venous blood at each occasion and place it into an EDTA tube. A total of 15 blood samples per study visit will be drawn for this study. Approximately 60 mL of blood will be drawn per subject if they complete both visits 2 and 3.

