## **5.4 Data Analysis & Statistics**

Separate independent sample t-tests will be used to evaluate the difference in average whole-body protein metabolism measured using stable isotope infusion versus oral sipping feeding method for both the low- and high-dose supplement. To assess validity of the oral method compared to the infusion method, total error (TE), standard error of the estimate (SEE), and Pearson's correlation coefficient, in addition to mean difference and 95% limits of agreement (LOA), will also be evaluated for PS, PB, and NB. Data using the infusion method was collected on a previous cohort of participants of similar demographics (n=8; 60% female; Age=21.4  $\pm$  0.5 years; Weight=73.8  $\pm$  4.8 kg; percent body fat=21.1  $\pm$  2.2%) using the same supplement product and dosing (4).

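### Does the absence of a dropout rule, with enrolment capped at 10, leave the oral-versus-infusion tests undefined?

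*Combined protocol and SAP*

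**What the plan says.** Section 4.0 reads: "Up to 10 subjects of any gender or ethnicity will be enrolled with a target of n=10, 50% female for study completion". Section 1.0 repeats the ceiling ("on up to ten younger, healthy subjects"). There is no sample-size calculation, dropout allowance or replacement rule.

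Incomplete participation is foreseen in three places. Section 4.4 pays subjects "for their amount based upon visits attended", section 5.1 gives the blood volume "if they complete both visits 2 and 3", and section 4.7 begins its provision with "In the event that subject dropouts or screening failures skew the balance of groups". The response in 4.7 concerns allocation only: "the groups will be modified toward the end of the enrollment period so that balance will be regained at the conclusion of the study".

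Section 5.4 sets the analysis: "Separate independent sample t-tests will be used to evaluate the difference in average whole-body protein metabolism", oral against infusion, at the low and at the high amount. The comparator already exists: "Data using the infusion method was collected on a previous cohort of participants of similar demographics", with n=8. Section 5.4 names no analysis set. Under section 4.5 each of Visits 2 and 3 carries one SP amount, so a subject who attends only one of them has data at one amount.

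**The concern.** With the cap equal to the target, any loss leaves fewer than 10 completers, and rebalancing the groups cannot bring the number back or split 9 subjects evenly between two orders. A subject lost after Visit 2 could be kept in the test for the amount taken (n=10) or set aside as a non-completer (n=9), and 5.4 does not say which.

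The stake is discretion more than precision. The infusion results are already in hand, and the blinding in section 4.6 covers the SP amount, not the tracer method. A decision taken after the oral results arrive might be taken knowing which way it moves the oral-minus-infusion difference, which bears on the study's only aim. Sections 4.5 and 4.7 also leave unclear when the group is assigned and whether a screening failure uses one of the 10 places.

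**Working it through.** **The plan's own figure.** n=10 has no stated derivation, so there is nothing to reproduce.

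**Inputs.** From the protocol: 10 oral subjects (4.0), 8 infusion subjects (5.4), two SP amounts (5.4), and three outcomes, PS, PB and NB. Section 5.4 names these outcomes for the agreement statistics; they are taken here to apply to the t-tests too. Assumed: two-sided alpha 0.05, equal SDs, normal data, loss unrelated to outcome.

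**Tests affected.** 3 outcomes × 2 amounts = 6. After one loss following Visit 2, the three tests at the missed amount have 9 oral subjects under either rule. The three at the amount taken have 10 or 9. So at most 3 of 6 depend on the rule.

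**Shift in the oral mean.** The SD of the difference between the mean of 10 and the mean of the same data without k subjects is √(1/(10−k) − 1/10).
- k=1: √(1/9 − 1/10) = 0.105 SD; × 1.96 = 0.207 SD.
- k=2 at the same amount: √(1/8 − 1/10) = 0.158 SD; × 1.96 = 0.310 SD.

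The standard error of the oral-minus-infusion difference is √(1/10 + 1/8) = 0.474 SD. For k=1 the typical shift is 0.105/0.474 = 22% of it, with a 95% limit of 0.207/0.474 = 44%.

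**Precision.** The 95% half-width is t(0.975, n+6) × √(1/n + 1/8).
- n=10: 2.120 × 0.474 = 1.006 SD.
- n=9: 2.131 × 0.486 = 1.036 SD.
- Ratio: 1.036/1.006 = 1.030, about 3% wider.

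Power at a true difference of 1 SD is 50.8% with 10 against 8 and 48.6% with 9 against 8.

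**How often the rules disagree at p<0.05** (simulation, pooled t-test, k subjects removed at random):

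| True difference (SD) | k=1 | k=2 |
|---|---|---|
| 0 | 2.1% | 3.2% |
| 0.5 | 4.6% | 6.8% |
| 1.0 | 7.5% | 11.4% |
| 1.42 | 5.6% | 9.2% |

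**Worst use of the discretion, k=1.** Suppose the analyst always reports whichever version suits. The share of tests significant under at least one rule is (a + b + d)/2, and under both is (a + b − d)/2, where a and b are the two rejection rates and d is the disagreement rate.
- No true difference: (5.0 + 5.0 + 2.1)/2 = 6.1% at the upper end; (5.0 + 5.0 − 2.1)/2 = 4.0% at the lower.
- True difference 1 SD: (50.8 + 48.6 − 7.5)/2 = 46.0% if non-significance is always preferred, against 50.8% with all 10.

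**Order balance.** Nine subjects split 5:4, so one order holds 5/9 of them instead of 1/2. The difference, 5/9 − 1/2 = 0.056, is the fraction of any period effect that would enter a mean at one amount because of the imbalance. The tests in 5.4 use neither order nor sex.

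**Which reading the text supports.** Section 5.4 specifies independent-sample tests, separately by amount. No within-subject contrast between amounts is planned, so a test at one amount needs nothing from the other visit. The completion wording in 4.0 is a recruitment target, and no section excludes a subject for missing a visit.

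**The case for a change.** The strongest case for acting is that the text is silent, the rule costs one sentence, and the comparator is already known. A loss is plausible: at assumed dropout of 5%, 10% or 20%, the chance of at least one among 10 is 1 − 0.95¹⁰ = 40%, 1 − 0.90¹⁰ = 65% or 1 − 0.80¹⁰ = 89%. If the agreement statistics are computed at the amount taken, the same choice would carry into them.

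The silence is real and the arithmetic holds. Three things reduce its weight. First, those chances rest on assumed rates and count every loss, whereas only attendance at exactly one of Visits 2 and 3 creates a choice; a loss before Visit 2 creates none. Second, section 4.6 keeps investigators blind to SP amount until the data have been analysed, and the comparison is specific to the amount. The direction of a keep-or-remove decision could be guessed but, if the blind holds, not confirmed beforehand. Third, the mean difference is one of several validity measures in 5.4, which sets no significance threshold; the verdict counts above apply a 0.05 criterion that the plan does not state.

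Whether withdrawals are replaced is the sponsor's design decision. The timing of assignment and the counting of screening failures are matters of wording with no shown effect on a result beyond the loss of a subject sized above.

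**Conclusion.** The concern does not call for a change. The plan leaves a policy unwritten, but its own analysis points to one answer: use every subject with data at the amount being tested. A completers-only reading is conceivable, yet nothing in the protocol supports it, so the tests are not undefined.

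Under random loss both rules are unbiased. One affected subject typically moves the oral mean by about 0.105 SD, well inside a 95% half-width of about 1 SD, and precision differs by 3%. Even deliberate selection between the rules would move the false-positive rate only from 5% to about 6%. Setting the cap equal to the target is a fair trade-off in a pilot where 10 and 50% female are targets, and exact order balance among 9 would gain almost nothing. These sizes assume equal SDs, normal data, a two-sided 0.05 level and loss unrelated to outcome; loss related to the response could shift the mean more.

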#### **4.1 Inclusion Criteria**

1. Aged 21-40 years.
2. Body weight of  $\leq$  80kg (176 pounds).

#### **4.2 Exclusion Criteria**

1. History Chronic kidney disease.
2. History of dairy allergy.
3. History of lactose intolerance.
4. History of whey allergy.
5. History of gastric reduction/bypass surgery.
6. Pregnant females.

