#### **4.3 Subject Recruitment and Consent**

Study staff will recruit subjects via word of mouth to friends, family and colleagues. Those who are interested will schedule Visit 1 with study staff, where the informed consent discussion and determination of eligibility will take place. Those who are eligible will have Visit 2 scheduled.

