#### **4.5 Study Visits**

Visit 1: This visit will take place at the UAMS RIOA.

At this visit, informed consent discussion is held. Study staff will use appropriate PPE with surgical mask and gloves. Subjects will also be required to wear a mask and if they do not have one, a mask will be provided to them by the study staff. If a subject enrolls, their eligibility will be determined. Eligible subjects will be randomized and be scheduled for Visit 2. A whole body DXA scan will be performed by study staff using the PI's machine for quantification of lean mass.

Visit 2: This visit will take place at the UAMS IOA. Subjects will be instructed to fast (consuming only water) from 10:00 P.M. the evening prior to this visit. Study nurse will insert an IV into the subject's preferred arm. At scheduled intervals, study staff will draw a ~2mL blood sample from the IV for research purposes, warming the arm by means of a heating pad or a heated plastic box. Blood will be transferred into a blood collection tube that contains EDTA, cooled on wet ice, centrifuged at  $\geq$  3000 RPM for  $\geq$  6 minutes, and have the resultant plasma transferred to a labelled cryo tube for freezing at  $\leq$  -80 degrees Centigrade.

After the initial blood sample is drawn, subjects will begin ingesting their oral isotope preparations, beginning with a priming dose (per study-specific stable isotope calculations). A timer will start when the priming dose is ingested. At 10-minute intervals, subjects will ingest a smaller volume of stable isotope preparations that will continue throughout the duration of the study visit (approximately 7 hours).

Approximately three hours after study initiations, subjects will ingest their randomly chosen amount of SP. Blood sample collection will continue at specific intervals throughout the remainder of Visit 2.

At the conclusion of the 7-hour study visit, the IV will be removed and a bandage placed over the site. Subjects will be provided with snacks and a beverage and be free to leave the site. Visit 3 is scheduled.

Visit 3: Subjects will come back to the RIOA having fasted overnight as for Visit 2. All study procedures undertaken during Visit 2 will be repeated at Visit 3, with subjects ingesting the remaining SP amount.

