## **6.4 Study Products**

The SP contains whey protein and may contain a small amount of lactose. Subjects with a known allergy or intolerance to whey protein, milk or lactose should not participate. In subjects with these allergies/intolerances, side or adverse effects of SP would include: abdominal pain, bloating, rash or hives, red and watery eyes, a runny nose, sneezing and coughing, diarrhea, nausea, and intestinal cramps.

The amino acids are naturally occurring required nutrients with no known adverse effects, even at much higher doses than will be used in this protocol. They are classified

as GRAS by the FDA. Study staff are responsible for accountability and dispensing of SP.

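### The exclusion list in 4.2 is narrower than the participation statement in 6.4: intolerance to whey protein, and milk intolerance other than lactose, are barred in one and absent from the other

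*Combined protocol and SAP*

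**What the plan says.** Section 4.2 has six numbered exclusions. Three concern reactions to the study product (SP): "History of dairy allergy", "History of lactose intolerance" and "History of whey allergy".

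Section 6.4, in the risk part of the same document, puts the restriction differently: "Subjects with a known allergy or intolerance to whey protein, milk or lactose should not participate". It goes on: "In subjects with these allergies/intolerances, side or adverse effects of SP would include: abdominal pain, bloating, rash or hives", and the list continues with further allergic and gut symptoms, among them diarrhea, nausea and intestinal cramps. It also says that SP contains whey protein and may contain a little lactose.

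Section 4.3 describes Visit 1 as the visit "where the informed consent discussion and determination of eligibility will take place". Neither 4.3 nor the Visit 1 text in 4.5 refers to 6.4. Under 4.5 each subject takes one SP amount at Visit 2 and returns for Visit 3, "with subjects ingesting the remaining SP amount".

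**The concern.** Both sections state who may take part, and they do not state the same thing. Section 6.4 applies allergy and intolerance alike to whey protein, milk and lactose. Section 4.2 pairs dairy and whey with allergy only, and uses intolerance only for lactose.

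The numbered list is what a screener would normally work from. Applied literally, it lets through a volunteer who reports intolerance to whey protein, or to milk for a reason other than lactose. The mismatch touches the ingredient that is certainly present: 4.2 excludes intolerance to lactose, which SP may contain in a small amount, but not intolerance to whey protein, which SP does contain.

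What is at stake is first the subject's safety and comfort, since 6.4 names the reactions it expects in such people and the crossover exposes each subject twice. Second, it is unclear whether such an enrolment would be eligible (by 4.2) or contrary to the protocol (by 6.4). Third, 4.0 allows up to 10 subjects and aims for 10 completers, so on its face a subject who withdrew after a reaction could not be replaced within that limit.

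**Working it through.** The point rests on a comparison of text. The plan gives no figure on it, so there is nothing to reproduce.

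**Step 1. Expand 6.4.** Two kinds of reaction (allergy, intolerance) and three substances (whey protein, milk, lactose) give 2 × 3 = 6 combinations.

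**Step 2. Set each against 4.2.**

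| Combination in 6.4 | Covered in 4.2? |
|---|---|
| Whey protein, allergy | Yes, whey allergy |
| Milk, allergy | Yes, as dairy allergy |
| Lactose, allergy | In effect, through dairy allergy |
| Lactose, intolerance | Yes, named |
| Whey protein, intolerance | Not named |
| Milk, intolerance | Only where it is lactose intolerance |

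Four of six are covered. One is absent, and one is covered only in part.

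**Step 3. Compare the wording in the other direction.** Section 4.2 asks about a history and uses the term dairy. Section 6.4 speaks of a known condition and uses the term milk. In these two respects 4.2 may be the broader text, so neither section simply contains the other.

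**Step 4. Follow the volunteer.** Eligibility is settled at Visit 1 (4.3, 4.5) with no pointer to 6.4. An admitted subject takes SP at Visit 2 and again at Visit 3, so there are two exposures.

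**Step 5. How likely is it to arise?** The documents give no prevalence. As a scale only, let p be the assumed share of otherwise eligible volunteers with one of the two unlisted conditions, and let all 10 places be filled (4.0). Then P(at least one among 10) = 1 − (1 − p)^10.

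| Assumed p | Expected number, 10p | P(at least one) |
|---|---|---|
| 0.5% | 0.05 | 4.9% |
| 1% | 0.1 | 9.6% |
| 2% | 0.2 | 18.3% |
| 5% | 0.5 | 40.1% |
| 10% | 1.0 | 65.1% |

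These values suppose that 4.2 alone is applied. They do not say how often such a subject would react. One such subject would be 1/10 = 10% of the sample.

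**Step 6. Where in the visit would a reaction fall?** SP is taken about three hours into a visit of about seven hours, so a reaction could affect only the remaining 7 − 3 = 4 hours or so. The earlier part of that visit comes before SP.

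**The case against.** The strongest reply is that 6.4 is part of the same protocol and says plainly that these people should not take part. Staff have that instruction even though it is not in the numbered list. Consent and eligibility are handled at the same visit, and section 7.0 has the person obtaining consent go through the risks. The consent form is not in the text available for review, so it cannot be said that volunteers are not asked. The three items in 4.2 also track the three substances in 6.4, so 4.2 may be meant as shorthand for the same restriction, and neither section defines a milk or whey intolerance apart from those three items. Finally, 6.5 requires the listed effects to be documented as adverse events, so a reaction would be recorded.

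Much of this stands. It means that such subjects can pass screening, not that they will, and that the gap is narrow. It does not make the two texts agree. Shorthand that leaves out intolerance to the main ingredient is still a different rule from the one in 6.4, and recording a reaction afterwards does not replace screening for it.

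A reader might go further and infer that a gut reaction would bias the tracer results, because the tracer is also taken by mouth: "At 10-minute intervals, subjects will ingest a smaller volume of stable isotope preparations that will continue throughout the duration of the study visit". The documents do not support that as a finding. Section 6.4 lists symptoms, and no section says that they alter tracer absorption or by how much. Any percentage put on such a bias would be invented.

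**Conclusion.** The inconsistency is established by the text: 4.2 does not name whey-protein intolerance or non-lactose milk intolerance, and 6.4 says that people with them should not participate. If 4.2 is applied as written, such a volunteer can be enrolled, would take SP twice, and would be at risk of the reactions in 6.4.

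The severity is minor. The gap covers one full combination and part of another out of six. Whether it bites depends on screeners using 4.2 without 6.4 and on a prevalence that the documents do not give. The probabilities above range from about 5% to 65% only because the assumed share ranges from 0.5% to 10%.

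The ground for acting is safety screening and a clear definition of eligibility. An effect on the kinetic data after SP is possible but not shown, and the conclusion does not rest on it. Nor do the documents show that any such subject will in fact be enrolled.

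**What to change.** Before enrolment, reconcile 4.2 and 6.4 so that the list used at Visit 1 and the statement in 6.4 cover the same conditions. Then ask about those conditions at Visit 1.

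Do this without dropping the history-based wording and the term dairy that 4.2 already has. Replacing the three items outright with the 6.4 sentence could lose a past allergy, or a dairy reaction, that the present list captures. A cross-reference between the two sections would help keep them aligned.

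The cost is about one line of protocol text and one screening question. The small downside is that an occasional volunteer may be excluded.
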